If a woman of childbearing age is enrolled as a subject and there has not been a pregnancy test during their current inpatient stay, a urine or blood pregnancy test will be performed. Pregnancy will not be allowed for this study as the drug is absorbed systemically and there are known risks to the fetus.

Section 4.0 Registration Procedure:

A prospective block randomized phase I/II two arm unblinded trial of a modified SGB protocol incorporated into Standard of Care vs UNMC standard of care Only for ARDS COVID-19 patients.

Subjects and/or Legally Authorize Representative (LAR) will be approached while subject is in the ICU/progressive care. If subject is unable to participate in the consenting process, the LAR will be contact via telephone and/or video chat. Consents will be sent to LAR electronically. PI and/or Sub-I will be present for all consenting process regardless is the ICF process takes place in person or video digital presence.

The randomization will be done by using *Stratified Permuted Block Randomization* in which sequential trial participants will be subdivided into the strata as indicated by their age-groups ie; 40-59, 60-74, 75-85 years and thereafter allocated to study group via block randomization within the strata so that the balance between age groups between the two study groups stays close to equal throughout the trial.

Section 5.0 Treatment Plan of Research Design:

A prospective block randomized phase I/II two arm unblinded trial of a modified SGB protocol incorporated into Standard of Care vs UNMC standard of care Only for ARDS COVID-19 patients.

Sixteen subjects will be enrolled. Eight in the control arm and eight in the intervention SGB arm.

Subjects will be identified on the COVID unit. The study will be explained to the subject and if the subject wishes to voluntarily participate, the ICF will be signed. If the subject is unable to sign consent, the LAR consent will be utilized. If LAR is not present, an electronic link to the consent will be sent to the LAR via email.

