The attending proceduralist will perform the SGB in the ICU/progressive care. ICU/progressive care nurse will provide patient monitoring and assistance during the procedure. Standard monitors and ACLS resuscitative equipment will be immediately available. A norepinephrine solution will be at bedside to treat potential hypotension associated with SGB. The SGB perineural catheter will be placed using standard sterile technique. Initial perineural bolus injection - clonidine 100 mcg, Decadron PF 5mg, and 0.25% bupivacaine 5 ml is delivered. A Cadd perineural infusion 0.2% bupivacaine will be initiated at 2ml/hr for 5 days. Acute pain service will discontinue infusion and remove the catheter after 5 days.

All adverse events and serious adverse events related to the SGB. All other adverse and serious adverse events, including death will be reported per IRB requirements. Laboratory analysis will be obtained at baseline (prior to block, baseline) and on day 1, day 3, and day 5. Labs include a cytokine panel (TNF-beta, IL-6, and IL-1 β), measurements of exhaled nitric oxide levels, and CRP (daily). Vital Parameter Analysis: Oxygenation, supplemental oxygen, type of respiratory support and need for mechanical ventilation, blood pressure i.e. hypotension requiring vasopressors and utilization of ECMO, heart rate, heart rhythm/new dysrhythmias, ICU/progressive care length of stay and discharge disposition will be collected from the EMR.

Control group: There will be no sham procedure for the control group. The control group will have nitric oxide levels performed once a day by a member of the research team. Lab draws will be drawn at the same frequency as the treatment group.

Treatment group:

The treatment group will have a SGB placed by the APS.

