We have computed stopping rules for safety, from a statistical standpoint, standpoint based on the known background rate to help support export opinion. The stopping rules for this study are based on the prospectively accumulated safety data collected from each individual patient and utilize the hypothesis testing approach. The idea is to rule out an observed event rate that is higher than the background event rate and to stop the trial if an excessive event rate is observed. For our plan to enroll 16 subjects, we assume (based on literature) that the background rate for the known risk of our experimental intervention is 10%. Based on this we have constructed a stopping rule plan (See Table below) based on the background rate of the main Serious Adverse Drug Reaction or Event SAE/ADR of 10%.

Our DSMB is empowered to stop the trial whenever they deem fit to protect the safety of patients. However, based on our plan, the DSMB will consider adopting a stopping rule that evaluates the rate of SAE/ADR after 5 enrollments,

and thereafter with each enrollment and SAE/ADR reported will require stopping/*suspension* of trial entry if the observed rate of SAE/ADR is sufficient to reject the null hypothesis that the true SAE/ADR proportion (P) is 10% or less in favor of the (one-sided) alternative hypothesis that the true SAE/ADR proportion is more than 10%. The table below depicts the stopping guidelines. Exact binomial methods are used to compute the p values and confidence limits. One-sided lower 90% confidence limit is calculated.

Number of Subjects Enrolled in the Study	Number of SAE/ADR Needed to Reject Null Hypothesis	Observed Rate of SAE/ADR (%)	One-sided p values	Lower 90% Confidence Limit
~5	2	40%	0.0815	11.22%
6-10	3	30%	0.0702	11.58%
11-15	4	27%	0.0556	12.18%
16-20	5	25%	0.0432	12.69%

Thus, for instance, if 2+ SAE/ADR events are observed in less than and equal to 5 subjects enrolled, the lower confidence limit of 11.22% will exceed the 10% background rate. The stopping rule for safety will be triggered and the study should be suspended/stopped at the discretion of the DSMB.

Section 11.0 Records to be kept: A list of all records, including flow sheets, data collection forms/instruments, summary and evaluation forms will be locked in the study coordinator's office. The subject list will be maintained by the study coordinator. The data from the electronic medical record will be retrieved and entered into the REDCAP database by research personnel.

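### The safety stopping table tests a 10% block risk against all enrolled patients, half of whom receive no block, and does not define which events count

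*Combined protocol and SAP*

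**What the plan says.** Section 10.0 (Stopping Rules) sets the null: "we assume (based on literature) that the background rate for the known risk of our experimental intervention is 10" per cent. It then describes the same figure as "the background rate of the main Serious Adverse Drug Reaction or Event SAE/ADR of 10" per cent. The test is exact binomial and one-sided, with a lower 90% confidence limit. No alpha is stated, but that limit implies a one-sided 10% level at each look.

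The first column of the table is headed "Number of Subjects Enrolled in the Study". The rows require 2 events at about 5 enrolled, 3 at 6–10, 4 at 11–15 and 5 at 16–20. The worked example also uses enrolled subjects: "if 2+ SAE/ADR events are observed in less than and equal to 5 subjects enrolled". On timing and status, "the DSMB will consider adopting a stopping rule that evaluates the rate of SAE/ADR after 5 enrollments", and then at each further enrolment and event.

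Section 5.0 gives the allocation: "Eight in the control arm and eight in the intervention SGB arm". Section 4.0 says that patients are "allocated to study group via block randomization within the strata", the strata being age groups. For the comparator, Section 5.0 states: "There will be no sham procedure for the control group".

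Section 9.0 has three overlapping lists of events. They govern stopping the procedure, removing the catheter, and withdrawing a patient for a directly block-related SAE. None is linked to the stopping table. Section 13.0 (DSMB) has the board assess relatedness and lets it request pooled or by-arm analyses for comparison with the stopping rules. It names no default.

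**The concern.** A 10% risk that belongs to the block is tested on a denominator in which half the patients cannot experience it. The table cannot be read as counting treated patients only, because 8 are treated and the rows run to 16–20.

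The text leans towards counting block-related events: the rate is tied to the intervention, and the DSMB assesses relatedness. No sentence says so. On that reading a 10% block risk is about 5% of all enrolled, so the printed thresholds are much stricter than their printed p values suggest. On the other reading, any-cause SAEs in both arms, the 10% is a block risk and not an SAE rate for ICU or progressive care patients.

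This is the only numerical trial-level safety rule in the document. Depending on a choice the plan does not make, it is either slow to react to block harm or liable to trigger on severity of illness alone.

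**Working it through.** **Inputs.** From Section 10.0: null rate 10%, one-sided exact binomial, lower 90% limit, thresholds 2/3/4/5, looks from the 5th enrolment. From Section 5.0: 8 SGB and 8 control patients. Assumed, because the documents do not say: permuted blocks of 4, immediate ascertainment, and at most one event per patient unless stated.

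**1. The plan's own figures.** p = P(X ≥ r | n, 0.10); the lower limit is the 10% quantile of Beta(r, n − r + 1). Taking n at the top of each row:

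| r/n | p | lower limit |
|---|---|---|
| 2/5 | 0.0815 | 11.22% |
| 3/10 | 0.0702 | 11.58% |
| 4/15 | 0.0556 | 12.18% |
| 5/20 | 0.0432 | 12.69% |

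All four rows reproduce. The arithmetic is right for a single group at a 10% rate.

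**2. The same thresholds on exposed patients, block-related events only.**

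| Enrolled | SGB patients | Threshold among SGB patients | Exact p | Printed p for the row |
|---|---|---|---|---|
| 5 | 2 or 3 | 2/2 or 2/3 | 0.0100 or 0.0280 | 0.0815 |
| 10 | 5 | 3/5 | 0.0086 | 0.0702 |
| 15 | 7 or 8 | 4/7 or 4/8 | 0.0027 or 0.0050 | 0.0556 |
| 16 | 8 | 5/8 (62.5%) | 0.0004 | 0.0432 |

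At 10 enrolled with 5 treated, 2 events are 2/5 of exposed patients. The first row treats 2/5 as a stop, but here the table asks for 3.

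**3. Chance of triggering, block-related events only, none in controls.** Exact sequential binomial recursion, averaged over all sequences of four blocks of 4:

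| True SGB event rate | 10% | 20% | 30% | 40% | 50% |
|---|---|---|---|---|---|
| Printed table, all enrolled | 2.5% | 11.4% | 27.1% | 47.0% | 67.0% |
| Same criterion on SGB arm (2 of up to 5, 3 of 6–8) | 9.1% | 30.8% | 55.4% | 75.9% | 89.5% |
| SGB-arm rule with matched false-trigger rate (3 of up to 7, 4 of 8) | 2.6% | 14.8% | 35.3% | 58.0% | 77.3% |
| All enrolled, null reset to 5% (2 up to 10, 3 at 11–16) | 9.2% | 31.0% | 55.6% | 76.1% | 89.5% |

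The last row shows that the loss comes from pairing a 10% null with a denominator on which the null rate is 5%.

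**4. Sensitivity.**
- Block size 2 or 8 gives 26.8% or 27.5% at the 30% rate; age-stratified blocks of 4 give about 28%.
- If events are counted and an assumed 25% of affected patients have two, simulation gives 10/26/45/65/80% across the five rates.
- If an assumed 10% of controls also have a countable event, the table triggers in 28/47/65/80% at SGB rates of 20/30/40/50%.

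**5. Any-cause reading.** With no block harm and the same SAE rate in all 16 patients, the printed table triggers in 12.9/46.7/77.5/93.5% at assumed rates of 10/20/30/40%. The documents give no such rate.

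**6. Minor threshold point.** The smallest rejecting count is 2 for n = 2–5, 3 for n = 6–11 and 4 for n = 12–18. So 3/11 (p = 0.0896, limit 10.5%) and 4/16 (p = 0.0684, limit 11.4%) already reject, while the table asks for 4 and 5. At n = 16, 5 events give p = 0.0170; the printed 0.0432 is for n = 20, beyond the planned 16. Correcting n = 11 alone moves the 27% in step 3 to 29%; correcting both moves it to 31%.

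**The case against.** The strongest reply is that the table is advisory. The DSMB may stop the trial whenever it sees fit, reviews weekly or at each potential SAE, and can ask for by-arm analyses. This stands as far as consequence goes: no patient's protection rests on the table alone, and the trigger probabilities above are not the trial's stopping probabilities. It does not settle the count or the denominator, because Section 13.0 sends any such analysis back to the same undefined table.

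Second, the contrast of 27% with 55% is mostly a difference in false-trigger level. This is correct. At a matched 2.6% level the cost of the denominator is 27% against 35%. But running near 2.5% when the 90% limit implies 10% is itself the fault, and it errs in the less protective direction.

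Third, the 27% requires no countable events in controls. If both arms share a 10% rate, the pooled table triggers in 12.9%, roughly as intended; with controls at 10% and SGB at 30% it triggers in 47%. Repeat events would also raise the figure. Withdrawal after a block-related SAE (Section 9.0) makes repeats less likely but does not exclude them. This shows how far the result depends on an unstated definition.

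Fourth, the n = 11 and n = 16 thresholds follow from using one threshold per grouped row: 3/12 gives p = 0.1109 and 4/19 gives p = 0.115, so neither would reject later in its row. That is a fair explanation, and the point is secondary.

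**Conclusion.** The concern holds and should be fixed. The null rate, the counted event and the denominator do not agree on either available reading. Counting block-related events, the printed table runs at about a 2.5% false-trigger rate instead of the implied 10%, and detects a 30% SGB event rate in about 27% of trials against 55% for the same criterion on the SGB arm (35% at a matched level). Counting any-cause SAEs, the 10% null is the wrong quantity, and triggering depends mainly on the background SAE rate.

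The exact p values for given counts need no assumption beyond the binomial model and the number exposed. The trigger probabilities rest on assumed blocks of 4, immediate ascertainment, one event per patient and, for the 27%, no countable control events. Block size hardly matters; control events and repeat events matter a good deal. The DSMB's discretion limits the practical harm.

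**What to change.** - Index the table on SGB-arm patients in whom the procedure was started, including those whose procedure was stopped. Count patients with at least one countable event, not events.
- Use 2 of up to 5 (2/5: p = 0.0815, limit 11.2%) and 3 of 6–8 (3/8: p = 0.0381, limit 14.7%). These are the thresholds of the present first two rows on a different denominator. Delete the rows above 8. The threshold of 3 remains valid up to 11 if stratified blocks put more than 8 patients in this arm.
- State that the rule applies from the second countable patient. If the first look were reworded as 5 treated, it would fall at about 10 enrolled. The overall trigger chance would be unchanged, but at a 30% rate the mean number treated at a trigger would be 5.4 instead of 4.2.
- Define the countable event and say whether DSMB-assessed relatedness is required. The sponsor should reconcile the three lists in Section 9.0 with this rule. If any-cause SAEs are meant, replace the 10% with a justified any-cause rate.
- In Section 13.0 (DSMB), make by-arm review against this table the default.

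The cost is one replaced table, about four sentences and notification of the DSMB. On the block-related reading, the chance of a false pause at a true 10% SGB rate rises from about 2.5% to about 9%, within the implied 10%.

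If a pooled table at a 10% null is kept, use 3 at n = 11 and 4 at n = 16, and print the n = 16 figures (4/16 = 25%, p = 0.0684, limit 11.4%). With a true 10% rate in all 16 patients, the cumulative false-stop chance rises from 12.9% to 14.6% (13.9% if only n = 11 is changed). This alone does not cure the block-related reading.

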- b) Differences in mean/median values for SGB vs SOC will be assessed at treatment day 5 - adjusted for baseline levels
- c) Differences in changes from baseline levels for SGB vs SOC as measured by comparison in slope trends;
- d) Differences in frequency of adverse events for SGB vs SOC over the study period from treatment through 90 day of follow up;

Secondarily,

- e) Differences between SGB vs SOC in *frequency and time to occurrence of cardiac arrhythmias*;
- f) Differences between SGB vs SOC in frequency of *need for and duration of use mechanical ventilation and/or extracorporeal membrane oxygenation (ECMO)*;
- g) Differences between SGB vs SOC in survival experience over treatment period through 90 -day discharge follow up

Sample Size issues:

For power computations we assume that SGB will particularly have an impact in reduction of inflammatory response as measured by IL-6. Looking at a meta-analyses of IL-6 values [Ulhaq ZS, Soraya GV. Interleukin-6 as a potential biomarker of COVID-19 progression. *Med Mal Infect.* 2020;50:382–383. doi: 10.1016/j.medmal.2020.04.002. 2020/04/08] and picking the largest of studies of COVID patients [Qin C, Zhou L, Hu Z, Zhang S, Yang S, Tao Y, et al. Dysregulation of immune response in patients with COVID-19 in Wuhan, China. *Clin Infect Dis* 2020, <http://dx.doi.org/10.1093/cid/ciaa248> [pii: ciaa248].], we estimate the overall mean (SD) IL-6 for COVID-19 patients to be 21 pg/mL (30.1). Using these estimates we see that a sample of 16 patients equally randomized into SGB (n=8) and SoC (n=8) would provide sufficient power to observe magnitude of differences in mean of IL-6 from as small as about 50 pg/mL and larger with 80% power at the 5% significance level assuming 2-sided hypothesis testing. (see Power Figure). The study [Liu MH, Tian J, Su YP, Wang T, Xiang Q, Wen L. Cervical sympathetic block regulates early systemic inflammatory response in severe trauma patients. *Med Sci Monitor.* 2013;19:194–201.], indicates that SGB is capable of eliciting reductions of IL-6 between groups and from baseline of magnitudes of greater than 100 pg/mL within 72hrs of first injection.

Section 7.0 Study Parameters:

Baseline Assessments

- Current Fio₂/PaO₂ ratio
- Current type of ventilation and oxygen use
- Current production of nitric oxide via Niox
- Current blood pressure and heart rate parameters
- Labs: IL-1beta, TNF-alpha, IL-6, ABG, CRP
- Chest x-ray
- Need for mechanical ventilation or other support

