Initial perineural bolus injection will include clonidine 100 mcg, decadron PF 5mg, and 0.25% bupivacaine 5 ml.

Perineural catheter:

Infusion of 0.2% bupivacaine will be initiated at 2ml/hr for 5 days.

All medications are FDA approved. Standard orders for perineural blocks will be entered into the EMR system. Pharmacy responsible for ICU/progressive care will dispense orders for the medication used in the SGB. Pharmacist in ICU/progressive care will fill Cadd pump infusion catheter once per day per standard procedure in the ICU/progressive care.

Section 9.0 Adverse Event Reporting Guidelines:

The initial procedure will be stopped and the patient will be withdrawn if any of the following occurs; vasopressor or unresponsive hypotension, intrathecal injection, pneumothorax, expanding hematoma, allergic reaction, or cardiac arrhythmias. For continuous infusions, the catheter will be removed and the patient will be withdrawn if any of the following occur: local systemic toxicity, seizure, catheter migration to intravascular or intrathecal space, expanding hematoma, vasopressor unresponsive hypotension, symptomatic bradycardia, insertion site infection. Any adverse events will be treated with Nebraska Medicine standard of care procedures. Subjects can also voluntarily withdraw at any time. The PI can also withdraw any subject that is not felt to be a suitable candidate for the study.

Serious adverse events directly related to block will result in withdrawal. Directly block related serious adverse events include: local systemic toxicity, seizure, serious allergic reaction, expanding hematoma, or catheter migration to intravascular or intrathecal space, insertion site infection. As well, patients will be withdrawn if the patient develops medication unresponsive bradycardia or hypotension. This may not be directly related to block but discontinuation of infusion may facilitate resuscitation of patient. Expected complications may include voice hoarseness, ipsilateral eyelid drooping, mild pain at site of catheter, and blurred vision. Occurrence of expected complications will not result in withdrawal from study unless demanded by the patient.

Section 10.0 Statistical Considerations:

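### The safety stopping table tests the block's 10% risk on finished outcomes but counts every enrolled subject, so unexposed, part-exposed and control subjects enter as completed non-events

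*Combined protocol and SAP*

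**What the plan says.** Section 10.0 (Stopping Rules) assumes that "the background rate for the known risk of our experimental intervention is 10" per cent and tests whether the true SAE/ADR proportion exceeds it. On the method it states: "Exact binomial methods are used to compute the p values and confidence limits". It adds: "One-sided lower 90% confidence limit is calculated".

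The first look "evaluates the rate of SAE/ADR after 5 enrollments". Later looks are triggered by enrolment as well as by events: "and thereafter with each enrollment and SAE/ADR reported will require stopping/*suspension* of trial entry if the observed rate of SAE/ADR is sufficient" for rejection of the null. The table's first column is headed "Number of Subjects Enrolled in the Study", and the worked example below the table also counts enrolled subjects.

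On exposure, Section 8.0 says: "Infusion of 0.2% bupivacaine will be initiated at 2ml/hr for 5 days". Section 5.0 allocates eight subjects to each arm, and the control arm has no block and no sham. Section 6.0, item d, sets the adverse-event comparison as "Differences in frequency of adverse events for SGB vs SOC over the study period from treatment through 90 day of follow up". No section limits the stopping-rule denominator to treated subjects, requires any minimum exposure, or says which arm's events form the numerator.

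**The concern.** An exact binomial test treats each of its n subjects as a finished yes/no result at the risk being tested. Here n is the enrolment count, read at the moment someone enrols. At such a look at least one subject has had no exposure: 1/5 = 20% of the denominator at five enrolled and 1/10 = 10% at ten, whatever the accrual rate. Subjects still on the infusion add to this. Controls cannot have a block-related event at all.

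The observed rate is therefore biased low for the risk that the 10% describes, and the required count can rise to the next row before the subjects who moved it have been exposed. Safety is the first-listed objective in Section 1.0, and this table is the plan's only numerical stopping rule. It is weakest when subjects enter quickly, which is when most would be exposed before a signal is acted on.

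**Working it through.** **1. Reproduce the table.** Inputs from Section 10.0: null rate 0.10, one-sided exact test, lower 90% limit. The p value is P(X ≥ r) for X ~ Binomial(n, 0.10). The limit is the 10th percentile of Beta(r, n − r + 1). At the top of each row:

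| r/n | p | Lower 90% limit |
|---|---|---|
| 2/5 | 0.0815 | 11.22% |
| 3/10 | 0.0702 | 11.58% |
| 4/15 | 0.0556 | 12.18% |
| 5/20 | 0.0432 | 12.69% |

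All eight figures match, so the table is a test on n complete outcomes.

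**2. A case of immature exposure.** Treat every subject as at risk, as the table does. Six are enrolled. Three have completed 5 days, one of them with an event, and three are on the infusion. At the fifth and sixth enrolments only one event is known, so nothing triggers. A second event then occurs in one of the three on infusion.
- The rule sees 2/6 (lower limit 9.26%) and asks for 3 events.
- Subjects who have completed or had an event number 3 + 1 = 4. For 2/4 the limit is 14.26%, above 10%, and the first row (2 events) is met.

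**3. A case of control dilution.** Ten are enrolled, five of them SGB, and the second block-related event is reported only now. On exposed subjects, 2/5 gives p = 0.0815 and meets the first row. On enrolled subjects, 2/10 gives p = 0.264 and the table asks for 3. At 16 enrolled with 8 SGB, 3/8 gives p = 0.0381 (limit 14.7%), while the table asks for 5.

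**4. Size of the immaturity effect, every subject at risk.** The plan gives neither accrual rate nor event timing, so both are assumed. The simulation has 16 subjects, exponential gaps with mean 7, 3.5 or 1 day, events uniform over 5 days, and 6,000 replicates. Looks start at the fifth enrolment and occur at every enrolment, event and 5-day completion, with the printed thresholds 2, 3, 4, 5. Each cell below shows the enrolled count, then the completed-or-event count.

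| Accrual | Share short of 5 days at sixth enrolment | Trigger at true 30% | Mean enrolled at trigger or end (true 30%) | Trigger at true 10% |
|---|---|---|---|---|
| 1 per week | 29% | 0.760 / 0.786 | 9.44 / 9.14 | 0.116 / 0.131 |
| 2 per week | 40% | 0.754 / 0.808 | 9.76 / 9.12 | 0.111 / 0.149 |
| 1 per day | 85% | 0.677 / 0.849 | 11.57 / 9.72 | 0.071 / 0.194 |

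The differences at 30% are 2.6, 5.4 and 17.2 points. Repeat runs give about 3, 6 and 18.

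**5. With the two arms modelled.** Blocks of four and block-related events only, at a true SGB rate of 30%. Across the three accrual rates the rule triggers in 16–26% of trials on all enrolled, 52–55% on SGB subjects who have started, and 55–61% on SGB subjects who have completed or had an event. The last step, which is immaturity alone, is about 1, 3 and 9 points. Most of the gap comes from counting controls.

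**The case against.** The strongest reply is that the table is only a guideline. The DSMB may stop the trial at any time, is said only to consider adopting the rule, reviews weekly or at each potential SAE (Section 13.0), and may ask for analyses by arm. This stands as mitigation, but Section 13.0 has those analyses reviewed against the specified stopping rules, so the denominator still has to be right.

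The loss from immaturity is small at one or two subjects per week. The 17–18 points need about 16 subjects in 16 days, which no section supports. Some harms listed in Section 9.0 arise at placement, and for those the count of started SGB subjects is already nearly mature. Counting events at once and non-events later is itself a bias, upward, so part of the gain in step 4 comes from a looser error rate: at one per day, false triggers go from 7% to 19%. All of this stands.

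A reader might infer that the rule would overlook two events among four completed subjects when two more have just entered. It would not. If the events fell within those 5 days, both preceded the fifth enrolment, and the rule fires there at 2/5 (11.22%).

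A reader might also infer that the rule is late whichever events are counted. The documents do not tie the numerator to an arm. If all SAEs in both arms count, the rule could trigger with no excess SGB risk: in 28–64% of trials with SGB at 10% and assumed control rates of 20–40%.

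**Conclusion.** The point holds. The table is an exact test of the intervention's 10% risk on finished outcomes, and the rule supplies it with all enrolled subjects, exposed or not. The printed p values and limits do not apply to those data, and DSMB discretion softens this without repairing it.

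That mismatch rests on the text alone. The size rests on assumed accrual, event timing, block size and true rate. Immature exposure alone costs about 2–3, 6 and 17–18 points of trigger probability (one per week, two per week, one per day) if every subject is at risk, and about 1, 3 and 9 within the SGB arm. Late triggering is shown for block-related events, which are what the 10% describes. The documents do not support a claim of large loss at any accrual rate, or that the DSMB must wait for the table.

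**What to change.** In Section 10.0, define numerator and denominator together. The numerator is SGB-arm subjects with an SAE/ADR. Relabel the first column *Number of SGB-treated subjects who have completed the 5-day period, ended the infusion early, or had an SAE/ADR*. Take the row from that number at each look, keep the look at each reported SAE/ADR, and count later events when they are reported.

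The restriction to the SGB arm is needed. If the column counted only infusion completers and subjects with events while both arms' events stayed in the numerator, an event-free control would never enter but a control with an SAE would enter at once. With a 10% rate in both arms, false triggers would then be about 29–34%.

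The cost is one column heading and a sentence or two, with no new data. The downside is a small upward bias, because events count at once and non-events only after 5 days. Simulated false triggers at a true 10% SGB rate are about 9–10%, rising to 11–12% at one per day under slightly different simulation settings, against 7–9% on SGB subjects who have started. A trigger leads to suspension or stopping at the DSMB's discretion. The 5-day window does not make the denominator mature for events that arise later, up to Day 90. Those enter only through the numerator, and the text should say so.

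### The safety stopping table asks for one event more than its own criterion at 11 and at 16 subjects, and its last row is computed for 20 subjects in a 16-subject trial

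*Combined protocol and SAP*

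**What the plan says.** Section 10.0 (Stopping Rules) assumes a 10% background rate and tests it one-sided. Entry is to be suspended or stopped when the data are "sufficient to reject the null hypothesis that the true SAE/ADR proportion (P) is 10% or less". On method it says: "Exact binomial methods are used to compute the p values and confidence limits", and then "One-sided lower 90% confidence limit is calculated". The worked example for the first row shows how the limit is used: the rule fires because "the lower confidence limit of 11.22% will exceed the 10% background rate". The first evaluation comes after 5 enrolments, and later ones come with each further enrolment and each reported event.

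The table groups enrolment into bands of about 5, 6-10, 11-15 and 16-20, requiring 2, 3, 4 and 5 events. Its last row reads "16-20 5 25% 0.0432 12.69" (the final figure is a percentage). Section 5.0 fixes the size of the trial: "Sixteen subjects will be enrolled". Section 10.0 repeats the figure of 16.

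**The concern.** A rule applied at every enrolment needs a threshold that is correct at every n. For a fixed number of events the evidence against 10% weakens as n grows. A count that just suffices at the top of a band can therefore be more than is needed at the bottom. The last band is the clearest case: 16 is the only value in it that this trial can reach, and it is the bottom of the band.

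At stake is whether the DSMB's only numerical safety guide fires when the plan's own test says it should. Where the table and the test disagree, the table is the less protective of the two.

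**Working it through.** **Inputs (Section 10.0 unless noted).** Background rate 10%; exact binomial; one-sided; lower 90% limit; trigger when that limit exceeds 10%; looks from n = 5 onwards; enrolment 16 (also Section 5.0). No numerical alpha is printed. A one-sided 90% limit implies alpha = 0.10, and the worked example uses it that way, so 0.10 is inferred.

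**Formulas.** For r events in n subjects, p = P(X ≥ r) with X ~ Binomial(n, 0.10). The lower limit is the one-sided Clopper-Pearson bound, i.e. the 0.10 quantile of Beta(r, n − r + 1).

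**Step 1: reproduce the table.** All four rows match, each at the top of its band:

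| r/n | p | Lower 90% limit |
|---|---|---|
| 2/5 | 0.0815 | 11.22% |
| 3/10 | 0.0702 | 11.58% |
| 4/15 | 0.0556 | 12.18% |
| 5/20 | 0.0432 | 12.69% |

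**Step 2: n = 16.** P(X ≤ 3) = 0.1853 + 0.3294 + 0.2745 + 0.1423 = 0.9316, so P(X ≥ 4) = 0.0684. The limit for 4/16 is 11.38%, above 10%, so 4 events meet the criterion. The table's 5 events at n = 16 have p = 0.0170, limit 16.06% and an observed rate of 5/16 = 31.25%, not the printed 25%.

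**Step 3: n = 11.** P(X ≤ 2) = 0.3138 + 0.3835 + 0.2131 = 0.9104, so P(X ≥ 3) = 0.0896. The limit for 3/11 is 10.48%, so 3 events meet the criterion. The table's 4 events have p = 0.0185 and limit 16.92%.

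**Step 4: the other values.** At n = 5, 6-10 and 12-15 the printed count equals the smallest count that meets the criterion.

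**Step 5: the rate column.** 4/16 is 25% and 3/11 is 27%, exactly the rates printed for those two bands. A reader using the rate column would trigger at these points; one using the count column would not.

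**Step 6: dependence on alpha.** Any alpha that accepts row 1 must be at least 0.0815. That exceeds 0.0684, so 4 at n = 16 follows without knowing alpha exactly. The n = 11 result needs alpha of at least 0.0896, which the 90% limit supplies. An alpha of 0.05 cannot be the rule, because the first three printed p values exceed it.

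**Step 7: size.** Probability of triggering by exact recursion over successive enrolments, assuming each subject's outcome is known at enrolment:

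| True rate | Printed table (looks 5-15 or 5-16) | Criterion, looks 5-15 | Criterion, looks 5-16 |
|---|---|---|---|
| 25% | 63.8% | 65.5% | 68.6% |
| 30% | 77.5% | 78.8% | 81.6% |

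Under this assumption the printed table gains nothing at n = 16: one more subject can add only one event, and 4 events by n = 15 would already have triggered. At a true 10%, over looks 5-16, the chance of a false trigger is 12.9% with the printed table and 14.6% with the criterion.

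**The case against.** The strongest reply is that little turns on this in practice.

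- **Entry is closed at n = 16.** The action named in Section 10.0 is chiefly suspension of entry, and after the 16th enrolment none is left to suspend. While entry is open only n = 11 differs, which is worth 1.3 to 1.7 points. This stands. What remains at n = 16 is DSMB review of any infusions still running (5 days, Section 8.0) and of adverse events collected to day 90 (Section 7.0).
- **The misses are narrow.** A fourth event reported at 12 to 15 enrolled triggers the printed table correctly, so the n = 16 miss needs the fourth event to be reported after the 16th enrolment. The n = 11 miss needs the third event to be reported while exactly 11 are enrolled. This also stands.
- **The table does not bind the DSMB.** Section 10.0 says the DSMB will consider adopting the rule and leaves stopping to its discretion. Section 13.0 has it reviewing weekly or upon each potential SAE, with analyses on request. This limits the harm but does not make the table agree with the test it is meant to represent.
- **Alpha is inferred.** True, and it matters only for n = 11.

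A reader might infer that the trial's final safety conclusion would be wrong, or that any trial ending with 4 events in 16 would be passed as safe. The documents support neither. The final safety analysis in Section 10.0 consists of descriptive summaries and a Fisher exact comparison between arms, and does not use this table. Whether 4 in 16 is missed depends on when the fourth event is reported.

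**Conclusion.** The inconsistency is real. The printed p values and limits are correct for 5, 10, 15 and 20 subjects; the fault lies in applying those counts to whole bands and in basing the last row on an n the trial cannot reach. The table is one event too strict at n = 16, for any alpha consistent with its own first row, and at n = 11 under the inferred alpha of 0.10.

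The loss is modest: 1.7 points at a true 25% and 1.3 at a true 30% while entry is open, or 4.8 and 4.1 points with the look at 16 included. These figures assume each outcome is known at enrolment. The documents give neither enrolment pace nor event timing. The opposite extreme, with every event judged only at n = 16, would give 37.0% against 59.5% at a true 25% and 55.0% against 75.4% at a true 30%. That is an outer bound, and it concerns review after entry has closed.

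This should be fixed, but it does not undermine the trial's safety monitoring as a whole.

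**What to change.** Replace the banded table with one row per n, computed at that n under the criterion already stated, and delete the 16-20 row:

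| n | Events | Rate | p | Lower 90% limit |
|---|---|---|---|---|
| 5 | 2 | 40.0% | 0.0815 | 11.22% |
| 6 | 3 | 50.0% | 0.0159 | 20.09% |
| 7 | 3 | 42.9% | 0.0257 | 16.96% |
| 8 | 3 | 37.5% | 0.0381 | 14.69% |
| 9 | 3 | 33.3% | 0.0530 | 12.95% |
| 10 | 3 | 30.0% | 0.0702 | 11.58% |
| 11 | 3 | 27.3% | 0.0896 | 10.48% |
| 12 | 4 | 33.3% | 0.0256 | 15.42% |
| 13 | 4 | 30.8% | 0.0342 | 14.16% |
| 14 | 4 | 28.6% | 0.0441 | 13.09% |
| 15 | 4 | 26.7% | 0.0556 | 12.18% |
| 16 | 4 | 25.0% | 0.0684 | 11.38% |

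State alpha = 0.10 in the text if that is what the 90% limit is meant to convey. The cost is one table and a rise of 1.7 points in the false-trigger chance at a true 10% (12.9% to 14.6%), which the sponsor and DSMB should accept knowingly. Printing the cumulative trigger probabilities would help the DSMB but is optional.
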